A phase 3, randomized, multicenter, open-label study evaluated the efficacy and safety of CPX-351 compared with conventional 7 + 3 (cytarabine for 7 days plus daunorubicin for 3 days) regimen in adult patients (60 to 75 years) with newly-diagnosed therapy-related Acute Myeloid Leukemia (tAML) or Acute Myeloid Leukemia with Myelodysplasia related changes (AML-MRC). The primary efficacy endpoint was overall survival (OS). The results showed OS was significantly greater in the CPX-351 group compared with the 7 + 3 group. The median OS was 9.56 months with CPX-351 and 5.95 months with 7 + 3 (Hazard Ratio [HR] 0.69; $P = 0.005$). Grade 3-5 non-hematologic

adverse events (AEs) occurring $\geq 5\%$ were similar between the two groups, except pneumonia (20% vs 15%) and bacteremia (10% vs 2%) were numerically higher in the CPX-351 compared with 7 + 3 groups, respectively. Also, median time to recovery of absolute neutrophil count (ANC) $\geq 500/\mu\text{L}$ and platelets $\geq 50,000/\mu\text{L}$ were longer in the CPX-351 group than 7 + 3 group⁹.

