14.0 STATISTICAL CONSIDERATIONS

In determining the sample size for the patient cohort, Minimax Simon's two-stage design (Simon, 1989) will be used. The null hypothesis that the true response rate is 0.1 will be tested against a one sided alternative. In the first stage, 7 patients will be accrued in each arm. If there are two or less responses in these 7 patients, the arm will be stopped. Interim analysis will be conducted to determine the benefit of applying the drug in each arm. In the winning arm, 11 additional patients will be accrued for a total of 18. The null hypothesis will be rejected if 4 or more responses are observed in 18 patients. This design yields a type I error rate of 0.1 and power of 0.8 when the true response rate is 0.3.

Descriptive statistical analysis will be calculated, including histograms or box-plots, proportions, range, means and standard deviations. Fisher's exact test and Wilcoxon rank test will be used in univariate analyses of categorical and continuous variables, respectively. Overall response (CR + CRI +) rate and its 95% CI. Given there is no adjustment for multiple comparisons, need to note the p-values from the univariate analyses will be nominal and not used to infer significance.

Toxicity Monitoring Rules

The following toxicity monitoring plan will terminate the trial early given evidence for excessive rates of toxicity with CPX-351 based on the method of Thall et al.¹⁴ Early termination will be applied to evaluate patients experiencing toxicity defined as any grade ≥ 3 non-hematologic AE that is determined to be at least possibly related to CPX-351. A total of 25 patients will be enrolled. The monitoring rules target a toxicity rate of 20% and assume a non-informative Beta (0.2, 0.8) prior distribution. The trial will stop early for toxicity if $\text{Pr}(\text{Toxicity Rate} > 0.20 | \text{data}) > 0.85$, i.e. stop early if the evidence for excessive toxicity (higher than 20%) for the target population given observed data is sufficiently high (probability > 0.85). Monitoring will be carried out

from the 3rd patient. Table 5 summarizes the resultant stopping boundaries and Table 6 summarizes the trial's operating characteristics.

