Table 5. Summary of early stopping boundaries from the 3rd patient. Target toxicity rate is 20%. Using prior of Beta (0.2, 0.8) and posterior probability threshold of 0.85. E.g. If 3 or more patients experience grade ≥ 3 non-hematologic AEs out of the first 6 patients, the trial will stop early. Whenever a grade ≥ 3 non-hematologic AE is observed, check this table to see if the boundary has been crossed. E.g. if a total of 4 grade ≥ 3 non-hematologic AEs has been observed on trial, and the total number of patients treated is 9 or less, then stop the trial for excessive toxicity.

Stop Early if #Patients Experienced grade ≥ 3 non-hematologic AE	2	3	4	5	5	6	7	8
Total #Patients Treated	3	6	9	12	15	18	21	24

Table 6. Summary of operating characteristics based on 10,000 simulations using boundaries in Table 5 for early stopping. For example, if the true toxicity rate is 20%, the probability of early stopping is 0.27, and if the true toxicity rate is 40%, the probability of early stopping is 0.88.

Scenario	True Toxicity Rate	Pr(Early Stop)	Average #Patients Treated	Average #Toxicities
1	- 0.10	0.05	23.2	2.3
2	0.20	0.27	19.8	4.0
3	0.30	0.62	14.6	4.4
4	0.40	0.88	9.8	3.9

Summary statistics of toxicity will be provided in frequencies and percentages. Toxicity rate will be estimated along with 95% CIs. Other statistical analyses will be carried out as appropriate.

REFERENCES

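### Table 5's caption drops the drug-attribution term, counts events instead of patients in one example, and prints fewer looks than the stated posterior rule implies

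*Combined protocol and SAP*

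**What the plan says.** The toxicity monitoring rules in Section 14.0 count patients with a non-hematologic AE of grade 3 or higher "that is determined to be at least possibly related to CPX-351". The prior is Beta(0.2, 0.8). The trial stops if the posterior probability that the toxicity rate exceeds 0.20 is above 0.85. Monitoring runs "from the 3rd patient. Table 5 summarizes the resultant stopping boundaries", and no interval between looks is given. The planned size is stated as "A total of 25 patients will be enrolled".

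Table 5 gives stopping counts 2, 3, 4, 5, 5, 6, 7, 8 at 3, 6, 9, 12, 15, 18, 21, 24 patients.
- Its row label counts patients ("Stop Early if #Patients Experienced grade"), as does the caption's first example.
- The caption tells staff that whenever such an event is seen they should "check this table to see if the boundary has been crossed".
- The second example takes four events: "AEs has been observed on trial, and the total number of patients treated is 9 or less, then stop the trial".
- Neither the label, the instruction nor either example mentions relation to CPX-351.

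Table 6 reports, for instance, that "if the true toxicity rate is 20%, the probability of early stopping is 0.27".

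On AE capture, Section 6.4 records no new-onset AEs during follow-up, apart from SAEs considered related or possibly related. Section 8.4 has all AEs reported through 30 days after the last dose.

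**The concern.** This is the trial's only toxicity stopping rule, and the caption is written so that staff can apply it without going back to the text. A Beta-binomial boundary needs one yes/no outcome per patient. Counting every event, or events unrelated to the drug, feeds it a larger number than it was built for. The trial could then close at a related-toxicity rate the rule is meant to tolerate.

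The look schedule works in the opposite direction. If the posterior criterion is checked at each event, as the text and caption suggest, some results call for stopping where the table says continue. The same data would lead to different decisions depending on which part of Section 14.0 is followed.

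**Working it through.** **Inputs** (Section 14.0): prior Beta(0.2, 0.8), target 0.20, threshold 0.85, 25 patients, and Tables 5 and 6.

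**Step 1: printed boundaries.** With s toxic patients among n, the posterior is Beta(0.2 + s, 0.8 + n − s). Stop if P(p > 0.20 | s, n) > 0.85.

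| n | s | posterior at s | at s − 1 |
|---|---|---|---|
| 3 | 2 | 0.932 | 0.617 |
| 6 | 3 | 0.928 | 0.721 |
| 9 | 4 | 0.934 | 0.785 |
| 12 | 5 | 0.943 | 0.829 |
| 15 | 5 | 0.863 | 0.692 |
| 18 | 6 | 0.888 | 0.752 |
| 21 | 7 | 0.909 | 0.799 |
| 24 | 8 | 0.925 | 0.835 |

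All eight entries reproduce.

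**Step 2: between the printed looks.** Under the caption's at-most reading, a count is compared with the next column to the right. The table then continues at these points, although the posterior exceeds 0.85: 2/4 (0.869), 3/7 (0.886), 4/10 (0.904), 4/11 (0.869), 6/19 (0.861), 7/22 (0.887), 7/23 (0.862).

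**Step 3: operating characteristics.** Exact recursion: carry the distribution of s forward one patient at a time, and at each look remove the probability at or above the boundary. Results are for true rates 10/20/30/40%.

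| Scheme | P(stop) | mean n |
|---|---|---|
| Table 6 as printed | 0.05/0.27/0.62/0.88 | 23.2/19.8/14.6/9.8 |
| Table 5 looks, at most 24 patients, crossing at 24 not counted | 0.046/0.270/0.626/0.883 | 23.2/19.8/14.6/9.8 |
| Table 5 looks, 25 patients | 0.046/0.276/0.645/0.900 | 24.1/20.6/15.0/9.9 |
| Posterior rule after every patient 3 to 24, 25 patients | 0.073/0.350/0.715/0.929 | 23.6/19.0/13.0/8.2 |

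Table 6 therefore describes per-patient counting with looks every three patients and a maximum of 24. Adding a look at 25 to the last scheme gives 0.073/0.352/0.721/0.934.

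**Step 4: attribution ignored.** Take a true related rate of 20% and assume a further 5/10/15% of patients have only unrelated grade 3 or higher non-hematologic events. The counted rate becomes 25/30/35%. With Table 5 looks and 25 patients, P(stop) rises from 0.276 to 0.460/0.645/0.797.

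**Step 5: events counted instead of patients.** Assume each affected patient has 1 + Poisson events with mean 1.25/1.5/2.0. P(stop), with Table 5 looks and 25 patients, is:
- at a 20% patient rate, 0.50/0.65/0.81, against 0.276;
- at a 10% patient rate, 0.16/0.27/0.44, against 0.046.

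**Step 6: an illustration from the protocol's own figures.** Section 1.2.2 reports for the phase III trial that grade 3–5 "pneumonia (20% vs 15%) and bacteremia (10% vs 2%) were numerically higher" on CPX-351. That trial was in AML, and no attribution is stated. Suppose 20% and 10% applied here, and let 0/2/5/10% of patients have both.
- Event counting gives P(stop) 0.645/0.644/0.650/0.670.
- Patient counting without attribution uses rates 30/28/25/20% and gives 0.645/0.573/0.460/0.276.

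**The case against.** The strongest reply is that Section 14.0 defines toxicity once and presents Table 5 as a summary of the resulting boundaries, so a shortened caption is not a second rule. Event counting appears in one example only. The row label, the first example and the definition all count patients, and Table 6 reproduces on per-patient counts. Section 8.1.3 requires an attribution for every AE, so the definition can be applied from recorded data. These points make misapplication less likely. They do not remove a worked example that uses the wrong unit in the text staff are told to use.

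On size, the inputs to Steps 4 and 5 are assumptions that no figure in the documents bounds. The phase III figures cannot isolate the attribution effect, because some of those infections might count as related. They illustrate what event counting can do and no more.

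On looks, the printed columns and Table 6 point to a check every three patients, which is a legitimate design. Applying the at-most reading after every patient leaves P(stop) at 0.046/0.276/0.645/0.900, so event-driven checking of the table does not disturb those probabilities. That reading still differs from the stated posterior criterion at the seven points in Step 2, and nowhere is a three-patient interval stated.

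The mismatch between Sections 6.4 and 8.4 concerns the collection window, and its effect on the rule is not quantified. It is secondary.

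**Conclusion.** The concern holds and should be corrected. Section 14.0 and the Table 5 caption do not describe the same stopping rule.

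- **Attribution and unit.** The direction is certain: the caption wording can only raise the count and so stop the trial sooner. At a 20% related rate, P(stop) goes from 0.28 to 0.46–0.80 or 0.50–0.81 under the assumed ranges. These sizes apply only if staff follow the caption rather than the definition.
- **Looks.** The effect runs the other way and needs no outside assumption. Table 5 gives 0.28 at a 20% rate, against 0.35 for the posterior rule checked at every patient from 3 to 24. At a 40% rate, mean n is 9.9 against 8.2.
- **Table 6.** It matches a maximum of 24 patients, not 25. Against Table 5 looks at 25 patients, P(stop) differs by about 0.025 at most and mean n by about 0.9 (24.1 − 23.2). This is minor and changes no boundary.
- **AE window.** Non-serious, related grade 3 or higher events between an early end of treatment and day 30 after the last dose are handled differently in Sections 6.4 and 8.4.

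**What to change.** Reconcile the definition with the table. Put the Section 14.0 patient-level wording, including the attribution term, into the row label, the check instruction and both examples, and express the second example as a number of patients. If a different definition is intended, change it everywhere.

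Then settle the looks. Either print boundaries for every n from 3 to 25 from the stated posterior rule, or state that looks occur only at 3, 6, ..., 24 patients and make the instruction to check at each event agree. Recompute Table 6 for 25 patients under the chosen schedule. As a secondary item, reconcile Sections 6.4 and 8.4 for non-serious new-onset AEs up to 30 days after the last dose.

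The cost is some rewording, one sentence on looks and one short recalculation, with no added patients. Choosing looks at every n raises P(stop) at a 20% rate from 0.28 to 0.35, which the investigators should accept knowingly.

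### Table 6 does not give the operating characteristics of the 25-patient trial with the Table 5 boundaries: early-stopping probabilities at 30% and 40% toxicity, and mean patients at 10% and 20%, are printed slightly too low

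*Combined protocol and SAP*

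**What the plan says.** Under Toxicity Monitoring Rules, Section 14.0 states "A total of 25 patients will be enrolled". It also says that "The monitoring rules target a toxicity rate of 20% and assume a non-informative Beta (0.2, 0.8) prior distribution", and it stops the trial when the posterior probability of a rate above 20% exceeds 0.85.

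Table 5 turns this into counts. Its rows read "Stop Early if #Patients Experienced grade ≥ 3 non-hematologic AE 2 3 4 5 5 6 7 8" and "Total #Patients Treated 3 6 9 12 15 18 21 24", so the last boundary is 8 patients with toxicity among 24 treated. The caption also tells the reader to consult the table each time an event occurs. Its example stops the trial at four events if nine or fewer patients have been treated.

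Table 6 is presented as a "Summary of operating characteristics based on 10,000 simulations using boundaries in Table 5 for early stopping". Its caption gives two worked figures: a stopping probability of 0.27 at a 20% rate, and "if the true toxicity rate is 40%, the probability of early stopping is 0.88". The section mentions neither a 24-patient maximum nor an inactive last boundary.

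**The concern.** Table 6 is the only evidence in the plan of how often the toxicity rule stops the trial and how many patients are treated before it does. A safety committee would judge the rule on these figures. If they belong to a different maximum sample size, or to a different set of active boundaries, the committee is assessing a rule other than the one in Table 5. It is also left unclear whether 8 of 24 counts as a stop.

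The first row already looks wrong. If the trial stops early only 5% of the time and otherwise treats 25 patients, an average of 23.2 is too low.

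**Working it through.** **Inputs (all Section 14.0).** Maximum 25 patients; prior Beta(0.2, 0.8); target rate 0.20; threshold 0.85; monitoring from the 3rd patient; boundaries 2, 3, 4, 5, 5, 6, 7, 8 at 3, 6, 9, 12, 15, 18, 21, 24 patients; 10,000 simulations.

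**Step 1. Table 5 reproduces.** After x toxicities in n patients the posterior is Beta(0.2 + x, 0.8 + n − x). The boundary is the smallest x with Pr(rate > 0.20) > 0.85. For example:

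- n = 3: 0.9316 at x = 2, 0.6165 at x = 1, so the boundary is 2.
- n = 12: 0.943 at x = 5, 0.8294 at x = 4, so the boundary is 5.
- n = 24: 0.9246 at x = 8, 0.8354 at x = 7, so the boundary is 8.

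All eight printed boundaries are confirmed.

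**Step 2. A hand check on row 1.** A printed 0.05 means a simulated proportion of at most 0.055. No trial stops before patient 3. With a maximum of 25, the simulated mean is therefore at least 0.945 × 25 + 0.055 × 3 = 23.8. Table 6 prints 23.2. The bound applies to the simulated runs themselves, so simulation error cannot explain the gap. With a maximum of 24 the bound is 0.945 × 24 + 0.055 × 3 = 22.8, and 23.2 is possible.

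**Step 3. Exact operating characteristics.** The number of toxicities is carried forward one patient at a time as a binomial count. Paths that reach a boundary at a check are removed. Pr(stop) is the total probability removed; mean patients is the sum of stopping point × probability, with completed trials counted at the maximum; mean toxicities is rate × mean patients.

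| Design | Quantity | 0.10 | 0.20 | 0.30 | 0.40 |
|---|---|---|---|---|---|
| Table 6 as printed | Pr(stop) | 0.05 | 0.27 | 0.62 | 0.88 |
| | Mean patients | 23.2 | 19.8 | 14.6 | 9.8 |
| | Mean toxicities | 2.3 | 4.0 | 4.4 | 3.9 |
| N = 25, checks at 3, 6, …, 24 | Pr(stop) | 0.046 | 0.276 | 0.645 | 0.900 |
| | Mean patients | 24.1 | 20.6 | 15.0 | 9.9 |
| | Mean toxicities | 2.4 | 4.1 | 4.5 | 4.0 |
| N = 25, Table 5 checked at each event from patient 3 | Pr(stop) | 0.046 | 0.276 | 0.645 | 0.900 |
| | Mean patients | 24.1 | 20.5 | 14.7 | 9.6 |
| | Mean toxicities | 2.4 | 4.1 | 4.4 | 3.8 |

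Pr(stop) is the same under both schedules because the count never falls. A boundary met between two listed sample sizes is still met at the next one, so checking at each event only brings the stop forward.

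**Step 4. Is it simulation noise?** For 10,000 runs the standard error of Pr(stop) is √(p(1 − p)/10,000).

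- Rate 0.30: standard error 0.0048; gap 0.6448 − 0.62 = 0.0248, or 5.2 standard errors. Allowing for rounding (0.625) leaves 0.0198, about 4.
- Rate 0.40: standard error 0.0030; gap 0.9002 − 0.88 = 0.0202, or 6.7 standard errors. Allowing for rounding (0.885) leaves 0.0152, about 5.
- Rate 0.20: gap 0.006 against a standard error of 0.0045, about 1.3. This agrees.
- Rate 0.10: 0.046 prints as 0.05. This agrees.

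With three-patient checks, the mean-patient gaps at 0.10, 0.20, 0.30 and 0.40 are about 22, 10, 4 and 1 standard errors.

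**Step 5. Which design does Table 6 match?**

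| Variant | Pr(stop) | Mean patients |
|---|---|---|
| N = 24, no stop counted at 24 | 0.046 / 0.270 / 0.626 / 0.883 | 23.2 / 19.8 / 14.6 / 9.8 |
| N = 24, stop counted at 24 | 0.046 / 0.276 / 0.645 / 0.900 | 23.2 / 19.8 / 14.6 / 9.8 |
| N = 25, no stop at 24 | 0.046 / 0.270 / 0.626 / 0.883 | 24.1 / 20.6 / 15.0 / 9.9 |

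Of these, only the first fits both columns. Its largest departure from print is 2 standard errors, before allowing for rounding.

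**The case against.** The strongest defence is that the effect is small and in the safe direction for stopping. The written rule stops slightly more often than the table says, no gap exceeds 2.5 points or one patient, and Table 5, which governs conduct, is right. In a 24-patient run, a crossing at the last patient is arguably not an early stop. All of this stands as to size. The last remark, however, explains the figures only by assuming a trial one patient smaller than the plan's.

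A second objection is that no single set of corrected means exists until the checking schedule is fixed. This also stands. The Table 5 caption describes event-triggered checking, which gives means of 14.7 and 9.6 at 30% and 40%, against 15.0 and 9.9 with checks every three patients. If the 0.85 posterior rule were instead applied after every patient from the 3rd to the 25th, Pr(stop) would be 0.07, 0.35, 0.72 and 0.93. The choice among these readings can move the figures more than the present discrepancy does.

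A reader might infer that Table 6 understates exposure throughout. The documents do not support that. With event-triggered checking, the mean at 40% is 9.6 against 9.8 printed, a slight overstatement, and at 30% the gap is only about 0.1 patient. A reader might also take it as established that a 24-patient simulation was run. That is inferred from the fit and stated nowhere.

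**Conclusion.** The point holds in a limited form. Table 6 does not follow from 25 patients and the Table 5 boundaries. The secure errors, under either way of checking Table 5, are:

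- Pr(stop) at 30% and 40%, printed about 2.5 and 2.0 points too low, including the caption's 0.88.
- Mean patients at 10% and 20%, printed about 0.9 and 0.7 to 0.8 too low.

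Pr(stop) at 10% and 20% needs no correction on grounds of error, although a rerun would print 0.28 rather than 0.27 at 20%. Whether the means at 30% and 40% are wrong, and in which direction, depends on the checking schedule.

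The result assumes independent patients with a common toxicity rate, outcomes known at each check, and a trial that runs to 25 unless the toxicity rule stops it. It is no evidence that the boundaries are wrong or that patients are less protected than stated. It is a reporting error in a safety table, worth correcting because it is cheap to correct.

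**What to change.** Rerun Table 6 for 25 patients with all eight boundaries active, including 8 at 24. State beside the table the maximum sample size, when the boundaries are checked, and whether a crossing at 24 counts as an early stop. Make the schedule agree with the Table 5 caption.

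Pr(stop) becomes 0.05, 0.28, 0.64 (0.645 to three decimals) and 0.90, and the caption's worked figures should follow. Mean patients and mean toxicities come from whichever of the two 25-patient designs in the first results table matches the stated schedule. If the sponsor intends the posterior rule to be applied after every patient, neither set applies and all columns need recomputing.

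If Table 5 is the rule as used, the cost is one table, one caption and a sentence on the schedule, with no change to the boundaries or to conduct.

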APPENDIX I
PERFORMANCE STATUS CRITERIA

ECOG Performance Status Scale		Karnofsky Performance Scale	
Grade	Description	Percent	Description
0	Normal activity. Full active, able to carry on all pre-disease performance without restriction.	100	Normal, no complaints, no evidence of disease.
		90	Able to carry on normal activity; minor signs or symptoms of disease.
1	Symptoms, but ambulatory. Restricted in physically strenuous activity, but ambulatory and able to carry out work of a light or sedentary nature (e.g., light housework, office work).	80	Normal activity with effort; some signs or symptoms of disease.
		70	Cares for self, unable to carry on normal activity or to do active work.
2	In bed < 50% of the time. Ambulatory and capable of all self-care, but unable to carry out any work activities. Up and about more than 50% of waking hours.	60	Requires occasional assistance, but is able to care for most of his/her needs.
		50	Requires considerable assistance and frequent medical care.
3	In bed > 50% of the time. Capable of only limited self-care, confined to bed or chair more than 50% of waking hours.	40	Disabled, requires special care and assistance.
		30	Severely disabled, hospitalization indicated. Death not imminent.
4	100% bedridden. Completely disabled. Cannot carry on any self-care. Totally confined to bed or chair.	20	Very sick, hospitalization indicated. Death not imminent.
		10	Moribund, fatal processes progressing rapidly.
5	Dead.	0	Dead

APPENDIX II: STUDY DESIGN TIME POINT DEFINITIONS

[figure not shown]
Study Time Points	Definitions
Screening	The screening period will occur over 28 days from the time of consent to day -1.
Induction Period	Day 1 ^a to D35 and/or count recovery
Disease Response	The D35 (+/-10 days) bone marrow.
Consolidation Period	The consolidation period is defined as C2D1 through C5D28. Patients who meet disease response criteria will be eligible to receive up to 4 cycles of consolidation therapy.
End of Treatment (EOT)	The day patients meets the defined EOT criteria (Table 1) and discontinues study treatment.
Follow up	Patient will be followed monthly as SOC every 30 days for the duration of 6 months after EOT.
End of Study (EOS)	The time the patient completes 1 year of follow up and/or patient's death, whichever were to occur first.
a: Day 1 is defined as the first dose of CPX-351	

